# 8.2.4 Schedule of Activities

Version Date: 06Jun2023 Page 11 of 19

Visit	1			Treatment			F/U	Unscheduled
XX7 1	_	2	3	4	5	6	7	
Week	-4 to -1	0	2	4	8	12	16	
Study day	-28 to -7	0	14	28	56	84	112	
Window in days			+/-3	+/-3	+/-3	+/-3	+/-3	
Screening/Baseline								
Informed Consent	X							
Review eligibility	X							
Medical history	X							
Detailed physical exam	X							
Demographics	X							
Confirm eligibility/Enroll		X						
Assessment								
Vital Signs	X	X	X	X	X	X	X	X
Interval history		X	X	X	X	X	X	X
Problem-focused Exam		X	X	X	X	X	X	X
Adverse Events		X	X	X	X	X	X	X
IGA		X	X	X	X	X		X
CLASI		X	X	X	X	X		X
Symptom Diary Review		X	X	X	X	X		X
Photography		X	X	X	X	X		X
Laboratory Testing		•						
CBC, CMP	X			X		X		X
Lipid panel	X					X		X
Urine Pregnancy	X	X		X	X	X		X
Treatment		•						
Weigh product		X	X	X	X	X		X
Dispense product (as needed)		X	X	X	X			X
Return product						X		X
Research Procedure								
Skin biopsy (optional)		X				X		X

# 8.2.5 Data Analysis

**Primary Endpoint:**  $A \ge 2$ -point reduction in IGA score at Week 12 compared to baseline.

*Secondary Endpoints*: The mean percentage change at Week 12 from baseline in CLASI, CLASI-A and CLASI-D scores; erythema (EI) and melanin indices (MI); and NRS for pain and pruritus.

Version Date: 06Jun2023 Page 12 of 19

*Exploratory Endpoints*: The change in inflammatory response, which includes the degree of inflammation, composition of inflammatory infiltrate, and interferon (IFN) signature.

### 9. RISKS TO SUBJECTS

# 9.1 Risks of Participation

As with any change in treatment, there is a risk of no change or worsening of disease. All subjects in this study will have active discoid lesions. This means that their current therapeutic regimen is inadequate to control their disease. Stopping any current topical therapies may lead to worsening of disease, but continuing the same treatment regimen will not lead to clearance of disease activity.

Ruxolitinib cream: Skin-related side effects of ruxolitinib 1.5% cream are rare, but local irritation, pain, itch, erythema, acne, or papular eruptions have been observed. Systemic side effects are not expected. In the largest trial of ruxolitinib cream to date (307 patients with atopic dermatitis, 3-20% BSA), no clinically significant laboratory changes were observed. As of June 28, 2020, a total of 2350 study participants have been exposed to topical ruxolitinib, with no serious adverse events or fatal or life-threatening serious adverse reactions identified as treatment-related (Incyte, Global Investigator's Brochure v9, Aug 2020). In this study, we anticipate few effects from systemic absorption since most patients with DLE have even less cutaneous involvement than in prior studies, typically only 1-2% BSA.

While systemic side effects have not been seen with topical ruxolitinib, and the amount applied to the skin will be limited given the small area of treatment, there is a theoretical risk of side effects that have been observed with much higher oral doses. The most common side effects of oral ruxolitinib include increased risk of infection, laboratory abnormalities (cytopenias, elevated transaminases, and elevated cholesterol & triglycerides), and mild neurologic and gastrointestinal symptoms (dizziness, headache, fatigue, insomnia, diarrhea, abdominal pain). Ruxolitinib is a pregnancy Category C drug.

As with any treatment, there is a small risk of an allergic reaction, though this has not been documented for ruxolitinib cream. There is no known risk of interaction between antimalarials and the study drug ruxolitinib.

Safety monitoring and mitigating risk associated with the use of ruxolitinib cream is addressed in Section 8.2.2.

Phlebotomy: The risks of having blood drawn include some pain with needle insertion and a small risk of bruising and/or infection at that site. Some people may get lightheaded, nauseous, or faint. The risks of phlebotomy will be reduced by its performance by trained phlebotomists.

Skin Biopsy: The skin punch biopsy procedure involves the momentary pain of the needle prick used to insert the local anesthetic. There is a low risk of having an allergic reaction to the anesthetic used (lidocaine with epinephrine), which could result in a rash, itching, swelling,

Version Date: 06Jun2023 Page 13 of 19

dizziness, or trouble breathing. There is also a low risk of skin discoloration, temporary bleeding/bruising, and infection. Subjects may have a scar at the site of each biopsy and there is a risk of delayed or difficult healing at the site of the biopsy. Standard precautions will be taken to minimize these risks. For example, the procedure will be performed by a trained professional who will discuss the risks of the procedure and actions to be taken in the event of a complication. Participants will be given a handout with wound care instructions and a number to call in the unlikely event that a complication arises. Additionally, subjects will be asked if they have any allergies to lidocaine. If the subject does not return for suture removal, a member of the study team will call the participant to check on the healing of the skin biopsy, and to see if there are additional questions or concerns.

# 9.2 Alternatives to Participation

Non-participation. Study participation is voluntary. Subjects are free to not participate or to withdraw at any time, without risking loss of present or future care that they would otherwise receive. If they choose not to participate, standard of care treatment will be available.

# 10. POTENTIAL BENEFITS TO SUBJECTS

There may or may not be any direct benefits for the participants who elect to enroll in this study. The potential direct benefits to the subjects include more frequent provider evaluation and management of their disease as well as potential efficacy of a new therapy (ruxolitinib).

# 11. COSTS FOR PARTICIPATION

There will be no additional costs to the subject due to this study in addition to those incurred as part of routine standard of care. Insurance will not be billed for any study-specific visits or procedures associated with the study. The normal costs related to the subject's care during the course of the study will be up to the subject's insurer:

- Physician visits outside of study visits
- Emergency room or urgent care visits
- Hospitalizations

### 12. PAYMENT FOR PARTICIPATION

Subjects enrolled in this protocol will receive \$35 for each visit and \$100 for each individual skin biopsy. Subjects will only be compensated for the activities they complete. For subjects who will complete all of the visits (#7) and optional biopsies (#2), the total compensation will be \$445. Subjects will be reimbursed \$35 if they are asked to come in for an unscheduled visit (and compensated an additional \$100 if a skin biopsy is performed).

For this study we use a subject payment system called Advarra Participant Payments. The system allows three ways to provide payment. Subjects can choose: a reloadable debit card; direct deposit; or mailed paper checks. The study team will help the subject create a "subject

Version Date: 06Jun2023 Page 14 of 19

profile" in the system. In order to provide payment, the subject will need to enter their name and date of birth into their subject profile which is required to set up a subject account and for customer service purposes. Depending on which payment method they choose, they may also need to enter their email address and banking information. If they already have an Advarra account (because they are in another study that uses this system), their existing profile will be used to provide payment. See the 'Information Sheet for Advarra Participant Payments" for additional information.

Payment received for participation in research is considered taxable income. If the subject receives payment for their participation in studies at the University of Rochester and its affiliates of \$600.00 or more in any one calendar year, the University is required to report this information to the Internal Revenue Service (IRS) in a 1099 (Miscellaneous Income) form. They will be sent a copy of this form and a copy will be sent to the IRS. Depending on the amount they are paid, they may be asked to submit a W-9 form, which includes their Social Security Number.

# 13. SUBJECT WITHDRAWALS

Subjects will be notified by the study coordinator and advised in the written informed consent provided that they have the right to withdraw from the study at any time without prejudice.

If participants of the study at any point meet the exclusion criteria established in this protocol, including pregnancy, study drug will be discontinued. In addition, study drug will be discontinued for any subject who experiences any of the following (per Common Terminology Criteria for Adverse Events v5.0):

- Grade 2 event in Cardiac Disorders
- Grade 3 event in any other System Organ Class

Current research does not suggest a treatment-associated increased risk for these events. Standard treatment will proceed as necessary to ensure optimal health for the subject. In this situation, long term data will no longer be collected, and only the data collected during the duration of participation of the clinical trial will be included in the data analysis and conclusions of the study.

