# 4. STUDY DESIGN

This is a 12-week, single-center, open-label study of ruxolitinib 1.5% cream for the treatment of discoid lupus. The primary endpoint is a ≥ 2-point reduction in Investigator's Global Assessment (IGA) score at Week 12 compared to baseline. Secondary endpoints at Week 12 include the mean percentage change from baseline in the Cutaneous Lupus Erythematosus Disease Area and Severity Index (CLASI), CLASI-A (activity) and CLASI-D (damage) scores; the change in erythema and pigmentation as determined by quantitative photographic analysis; and the change in numeric rating scale (NRS) for pain and pruritus. Exploratory endpoints of skin biopsies will evaluate cellular and molecular features of discoid lesions preand post-treatment for 1) predictors of treatment response, and 2) treatment response to ruxolitinib. Quantitative and qualitative measures of the cutaneous inflammatory response, including evaluation of the immune cell infiltrate and IFN signature, will be assessed.

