# 8.2 Study Procedures

Clinical assessments, safety procedures, and research procedures will be performed as outlined below per the schedule of activities. In the event that one of these is not able to be completed, disease activity increases or other concerns arise, the subject may be asked to return to the clinic for an "unscheduled visit" to reassess the subject and perform as needed any clinical assessments, safety procedures, or research procedures as outlined below.

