# **16.2 SAE Reporting to Incyte**

The Principal Investigator (PI) must report all Serious Adverse Events (SAEs) to Incyte within 24 hours of learning of an event, regardless of the PI's causality assessment. This notification should be provided on a completed Serious Adverse Event (SAE) form. SAE reporting for each subject begins the day the informed consent is signed by the patient and within 30 days after subject has completed or discontinued from the study or has taken last dose of the study drug, or as described in the protocol.

SAEs, occurring using Incyte study drug, are reported in accordance with the effective protocol. SAEs occurring with any other commercial drug are reported to the manufacturer of that drug in accordance with regulations and protocol.

Initial SAEs and/or subsequent follow-up reports should be reported via email to [contact] or fax (+) [name]. SAE reports should be for a single subject. SAE forms should be sent with a cover sheet and any additional attachments.

All adverse event information is reported to Incyte on the Principal Investigator's/Institution's Adverse Event Report Form, or a CIOMS-I or MedWatch Form FDA 3500A, or on an Adverse Event Report Form which may be provided by Incyte upon request. The Principal Investigator does not provide medical records (e.g., discharge summary) to Incyte, unless specifically requested.

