# 16.3 Reporting of Pregnancy to Incyte

An "Initial Pregnancy Report" or equivalent must be completed in full and emailed to [contact] or faxed to (+) [name] within 24 hours of discovery of a pregnancy of a subject who has taken the Incyte product or the pregnancy of a partner for a subject who has taken the Incyte product. The "Follow-up Pregnancy Report Form" or equivalent must be completed and emailed to [contact] or faxed to (+) [name] within 30 days after delivery, so that Incyte is provided with information regarding the outcome of the pregnancy. If the pregnancy results in any events which meet

Version Date: 06Jun2023 Page 17 of 19

the serious criteria (i.e., miscarriage or termination), the SAE reporting process needs to be followed and the timelines associated with a SAE should be followed.

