# 17. DATA ANALYSIS PLAN

This exploratory study has a sample size of 15 subjects. Given the small sample size, a robust statistical analysis will be limited. The primary endpoint will be a  $\geq$  2-point reduction in IGA score. The mean percentage change from baseline will be assessed for the secondary endpoints (CLASI, CLASI-A, CLASI-D, NRS, EI, MI). Statistical analysis of exploratory endpoints comparing skin tissue before and after ruxolitinib treatment will be performed in accordance with the technique being used (histology, flow cytometry, RNAseq). Analyses of DLE histology (H&E, IHC, IFM) will include common histologic features (follicular plugging, interface change, etc.), cell counts of the immune infiltrate, and markers of IFN response. Flow cytometric analysis will evaluate the immune infiltrate, including T and B cell subsets. The focus of the RNAseq analysis will be on interferon expression, though other analyses may be performed. Differences will be considered significant at p < 0.05.

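### Section 13 appears to end scheduled assessments when study drug is stopped, and Section 17 gives no denominator or rule for the missing Week 12 IGA

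*Combined protocol and SAP*

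**What the plan says.** **Endpoint.** Sections 4 and 8.2.5 define the primary endpoint as at least a 2-point "reduction in IGA score at Week 12 compared to baseline". Section 17 repeats the 2-point criterion and gives a sample size of 15. It names no summary measure, analysis set or denominator, and does not say how a subject without a Week 12 IGA counts.

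**Drug stop.** Section 13 stops study drug for any subject who comes to meet an exclusion criterion (pregnancy included), has a Grade 2 cardiac event, or has a Grade 3 event in any other class. It continues: "Standard treatment will proceed as necessary to ensure optimal health for the subject". After such a stop, "long term data will no longer be collected, and only the data collected during the duration of participation of the clinical trial will be included" for analysis. Neither the long-term data nor the period of participation is defined.

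**Visits.** The schedule in Section 8.2.4 places the IGA at Weeks 0, 2, 4, 8 and 12, and a safety follow-up at Week 16. It has no early-termination visit. Its Unscheduled column does include an IGA, but Section 8.2 makes such a visit optional ("the subject may be asked to return to the clinic for an" unscheduled visit) and does not let its IGA stand in for Week 12.

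**Reporting that continues.** Under Section 16.2, serious adverse events go to the drug supplier "within 30 days after subject has completed or discontinued from the study or has taken last dose of the study drug". Under Section 16.3, a pregnancy follow-up report is due "within 30 days after delivery, so that Incyte is provided with information regarding the outcome of the pregnancy".

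**Counts.** Section 4.1.1 counts 15 at consent, while the schedule confirms eligibility and enrols at Visit 2. Section 16.1 tracks consented, enrolled and completed subjects separately.

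**The concern.** The stopping list consists largely of adverse events. If stopping the drug also ends the visits, the plan's own rule removes the primary outcome for exactly those subjects, along with their Week 16 safety visit. That loss is not random with respect to how treatment went.

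Section 17 does not close the gap. Once the open-label results are known, the team could report responders among those with a Week 12 IGA, or responders among all who were treated. The responder proportion is the natural headline of a single-arm study of this size, and each of 15 subjects carries 100/15 = 6.7 percentage points.

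**Working it through.** **No figure to reproduce.** The documents give no power, null rate, target rate, expected stop rate or named test for the primary endpoint. The check is therefore a comparison of texts and then an illustration.

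**Step 1: the texts together.** Section 7.1 is clear for one case: after withdrawal of consent nothing new is collected. Section 13 deals with a different case, a drug stop without withdrawal of consent. It sits under the heading on withdrawals and limits the analysis to what was gathered during participation, so the natural reading is that the remaining assessments end. Sections 16.2 and 16.3 show that safety and pregnancy reporting go on, and Section 16.2 lists leaving the study separately from the last dose. Neither section concerns the IGA. On the natural reading, a subject stopped at Week 4, for example, has IGAs at Weeks 0, 2 and 4, perhaps one unscheduled IGA, and none at Week 12.

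**Step 2: the gap between the two analyses left open.** Inputs: N = 15 treated (Section 17's figure, assumed to be the number treated); s = subjects stopped with no Week 12 IGA (assumed); x = responders among those with a Week 12 IGA (assumed).

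- Completers-only rate: x/(N − s)
- All treated, missing as non-response: x/N
- Gap: x/(N − s) − x/N = x·s/[N(N − s)], which is never negative

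Exact (Clopper-Pearson) 95% intervals are in brackets.

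| x | s | Completers only | All treated | Gap (points) |
|---|---|---|---|---|
| 4 | 1 | 4/14 = 28.6% (8.4–58.1) | 4/15 = 26.7% (7.8–55.1) | 1.9 |
| 4 | 3 | 4/12 = 33.3% (9.9–65.1) | 4/15 = 26.7% (7.8–55.1) | 6.7 |
| 6 | 1 | 6/14 = 42.9% (17.7–71.1) | 6/15 = 40.0% (16.3–67.7) | 2.9 |
| 6 | 3 | 6/12 = 50.0% (21.1–78.9) | 6/15 = 40.0% (16.3–67.7) | 10.0 |
| 8 | 1 | 8/14 = 57.1% (28.9–82.3) | 8/15 = 53.3% (26.6–78.7) | 3.8 |
| 8 | 3 | 8/12 = 66.7% (34.9–90.1) | 8/15 = 53.3% (26.6–78.7) | 13.3 |

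With s = 0 the gap is zero. In every row the intervals overlap widely.

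**Step 3: a different quantity, the error against the rate that full follow-up would show.** Let r be the number of stopped subjects whose Week 12 IGA, if collected, would have shown response. The rate with full follow-up is (x + r)/N. For x = 6 and s = 3:

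| r | Full follow-up | Completers only minus full | Missing as non-response minus full |
|---|---|---|---|
| 0 | 6/15 = 40.0% | +10.0 | 0.0 |
| 1 | 7/15 = 46.7% | +3.3 | −6.7 |
| 2 | 8/15 = 53.3% | −3.3 | −13.3 |
| 3 | 9/15 = 60.0% | −10.0 | −20.0 |

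The negative entries are errors against data that would not be collected on the natural reading. They are not differences between the two analyses in Step 2. The completers-only error is (s/N) × (completer response rate − stopper response rate), so its sign depends on which group responds more often. Counting missing as non-response can only understate this rate. Neither convention replaces having the Week 12 IGA.

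**The case against.** **The wording may already be a rule.** Section 13 says which data enter the analysis. That is so, but it does not say whether a subject with IGAs to Week 8 and none at Week 12 is a non-responder, is left out, or is judged on an earlier value.

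**An IGA at the stop is provided for.** The Unscheduled column covers IGA, CLASI, photography, laboratory tests and return of product. This softens the point: such a visit could document a subject's state at the stop. It remains optional and is not the Week 12 endpoint.

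**The effect may be nil.** Section 13 states that current research does not suggest a treatment-related increase in the stopping events, and nothing in the documents supports 3 stops in 15. Those events stop the drug whatever their cause, so a low rate is not established either. With one stop, the gap in the table is under 4 points, less than one subject's weight.

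**The study is exploratory.** Section 17 concedes: "Given the small sample size, a robust statistical analysis will be limited". There is no threshold to pass, and a report that gives its counts lets a reader compute either rate. This stands and sets the severity. It does not explain leaving the denominator open.

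**Non-response for missing is only a convention.** Correct, as Step 3 shows. This is why continued assessment comes first in the fix.

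**Stronger readings that the documents do not support.** A reader might infer that all data collection stops with the drug; Sections 16.2 and 16.3 contradict that. A reader might infer that a completers-only analysis is planned, or that the reported rate will be inflated. Section 17 chooses no analysis, and the direction of error depends on how stopped subjects would have fared. Nor does Section 13 state outright that Week 12 is lost. That is its natural reading, with key terms undefined.

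**Conclusion.** The point holds as a minor one. On its natural reading, Section 13 gives up the Week 12 IGA and the Week 16 visit for subjects taken off drug, and Section 17 does not say how they count. A rate based only on subjects with a Week 12 IGA is too high if those stopped respond less often than completers, and too low if they respond more often.

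With 15 treated and 6 responders, the choice of denominator is worth 2.9 points for one stop and 10.0 points for three. These sizes rest on assumed stops and responders, and on all 15 being treated. They are small beside the width of the exact intervals, and no decision rule depends on them. The case for change is that the remedy is cheap and removes a choice that would otherwise be made with the data in view.

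**What to change.** 1. **Section 13.** Replace the sentence on long-term data. State that, unless consent is withdrawn, the already scheduled assessments through Weeks 12 and 16 continue after study drug is stopped. The stopping rules stay as they are.
2. **Section 17.** Define the primary denominator as every subject who applied study drug at least once. Count a missing Week 12 IGA as non-response. Report responders/N with an exact 95% confidence interval, give the completer rate as a sensitivity analysis, and state the numbers consented, treated and missing at Week 12.
3. **For the investigator to state in advance.** Say whether a Week 12 IGA seen after a drug stop, or after other treatment for discoid lupus, counts as observed or as non-response. Section 13 foresees standard treatment after a stop, so the question will arise. Either answer defines a legitimate estimand.

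The cost is a short amendment with the re-consent that Section 7.1 requires, a few already planned visits for subjects off drug, and possibly a slightly lower reported rate.

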### 14. PRIVACY AND CONFIDENTIALITY OF SUBJECTS AND RESEARCH DATA

Steps to ensure privacy and confidentiality of subjects and research data will include:

- The PI will be responsible for all aspects of this study, including privacy and confidentiality of subjects and research data.
- All study personnel will be appropriately trained in Good Clinical Practice.
- Study investigators or coordinators will meet with subjects in a private room, where they will conduct all aspects of this study that involves direct subject interaction.

Version Date: 06Jun2023 Page 15 of 19

- Subjects will not be re-contacted without prior consent. During the process of consent, subjects will be given the option to be re-contacted regarding opportunities to participate in future studies.
- All electronic and physical documentation that includes protected health information (PHI) will be stored in files and/or folders with access limited to authorized study personnel only.
- Physical files will be kept in a locked secure area of the URMC Dermatology CTU.
- Computers on which electronic PHI data is accessed will be password protected and will not be left unattended while in use.
- Passwords and system IDs will not be shared.
- Physical security of computers/files will be maintained.
- Subjects and samples will be assigned a unique code to facilitate deidentification of the data. Codes will not be generated from existing identifiers, such as initials or enrollment date.
- Only authorized study personnel will have access to data containing PHI.
- Other research personnel conducting experiments on tissue samples and analyzing data will have access to deidentified samples and data only.
- Data will be stored for at least 6 years after the completion of the study, or for at least two years following marketing approval (or, if not approved, 2 years following shipment and delivery of the investigational product is discontinued), whichever is longer.

